8.2 Laboratory Procedures

Collection of Biomarker Samples:

Cytokine levels in serum: such as IFN- α , TNF- α , IL-17, IL-6, IL-1, IL-4, IL-2, IL-10, GM-CSF at baseline, weekly before every dose and 12-24 h after dose in Arm A. In Arm B, same panel will be assessed at baseline, 12 to 24 h and approx. 7 and 14 days after randomization.

Immunophenotyping in whole blood samples: T_{eff} cells (CD4, CD8, T_{reg} cells), TH17 and macrophage activated cells will be analysed at baseline, 12-24 h after 1st dose and 24h after the second/last dose in Arm A and at baseline, 12-24 h and approx. 7 days after randomization in Arm B.

Blood sample collections and handling instructions:

Two sets of sample collection are required:

1) Serum Sample

Samples to be collected: Blood 4-5 ml; (approx. 2-2.5 ml serum can be collected from blood)

Time points: Refer to section 8.1: Schedule of Study Visits and Procedures

Storage of sample: Serum separation will be performed at the Site/Clinic.

For each visit, serum samples should be immediately aliquoted into 2 vials of approx. 1 ml each and then stored at -70° C \pm 15° C or dry ice. Transportation should take place in dry ice only. Once at CRO the samples should be stored frozen at -80° C till used for batch analysis. This samples will be used for cytokines/chemokines.

Note: if -20 freezers are only available, then samples to be shipped within 24h in -80° C.

To be performed at:

Syngene International Ltd.

[name]
[name]
Karnataka, India

2)Whole blood Collection:

Additionally, approximately 4ml of blood is to be drawn for immunophenotyping. . Sample should be stored at 2-8 °C. **NOT FROZEN** and shipped to Syngene international Ltd or analysed locally.

The sample has to be shipped and should reach Syngene or local lab for analysis within 48 h.

Time points: Refer to section 8.1: Schedule of Study Visits and Procedures

Specific details will be included in the Laboratory manual/instruction document sent to the sites.

9. Safety Monitoring

Adverse Events and Safety Reporting

For the evaluation of safety, all the evidences of adverse events occurring during the study will be considered. The clinical laboratory tests will be conducted at local labs as and when necessary for safety evaluation. Any investigation, at any time during the study may be conducted at the local lab as per investigator's discretion, in order to monitor safety. Definitions of adverse events and safety reporting for SAEs and SUSARs will be as per regulatory requirements for marketed products (Refer Appendix 3 for details on definitions and reporting that Investigators must follow to satisfy regulatory requirements and ensure patient safety and well-being).

Special Precautions

In general, according to previous data, ALZUMAbTM is safe and well tolerated. However, it is recommended that investigators should exercise caution before administering ALZUMAbTM in subjects with a history of recurrent infections, or underlying conditions which may predispose them to infections. Subjects who develop a new infection while undergoing treatment with ALZUMAbTM should be monitored closely and treated according to standard treatment guidelines. While previous clinical study data has not revealed the incidence of opportunistic infections, it is recommended that Investigators be watchful for occurrence of tuberculosis and opportunistic infections like candidiasis. Administration of ALZUMAbTM should be discontinued if a subject develops a serious infection (other than COVID19). In case a reactivation of latent tuberculosis occurs in study subjects during the clinical study, immediate treatment in accordance with standard medical practice should be instituted and the subjects should be withdrawn from the study.

10.Data Handling Procedures

Source Documents

Source data is all information, original records of clinical findings, observations, or other activities in a clinical study necessary for the reconstruction and evaluation of the study. Source data are contained in source documents. Examples of these original documents, and data records include: hospital records, clinical and office charts, laboratory notes, memoranda, subject's diaries or evaluation checklists, pharmacy dispensing records, recorded data from automated instruments, copies or transcriptions certified after verification as being accurate and complete, microfiches, photographic negatives, microfilm or magnetic media, x-rays, subject files, and records kept at the pharmacy, at the laboratories, and at medico-technical departments involved in the clinical study.

Location of Data

All records and documents pertaining to the study will be maintained in the permanent files of the Investigator and will be available for inspection by the authorized party at any time.

Statistical Analysis

In general, continuous variables is summarized using descriptive statistics such as mean, standard deviation, 95% confidence interval (CI), minimum, and maximum. Categorical variables are summarized using proportions (counts and percentages). All statistical tests will be performed at 5% level of significance (two-sided test) and p-value<0.05 considered statistically significant (if necessary). All statistical analysis will be performed using SAS® (version 9.4 or higher) system software (SAS Institute Inc., USA)/or R/or EAST/or NCSS software.

11.Administrative Procedures

Ethics and Good Clinical Practice

This research will be carried out in accordance with the clinical research guidelines established by the basic principles defined in the revised New Drugs and Clinical Trials 2019, India and the principles enunciated in the Declaration of Helsinki [Ethical Principles for Medical Research Involving Human Subjects, revised, October 2013]. The investigator is responsible for overall activities at the center in accordance with Indian ICH-GCP guidelines, current New Drugs and Clinical Trials 2019 and ethical guidelines for biomedical research on human subjects issued by ICMR.

Interim study report - Data will be provided to DSMB (constituted prior to first patient screened) on a periodic basis. Based on DSMB recommendation, interim clinical study report may be prepared and submitted to DCGI/regulatory agencies.

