6. Change in inflammatory markers like CRP (C-reactive protein) level, d-Dimer, ferritin etc. [Time Frame: Arm A; baseline, during treatment (Before every dose and 12 to 24 h after every dose) up to 1 month, Arm B: baseline, 12 to 24 h and approx. 7 and 14 days after randomization]

Secondary Outcome Measures:

1. Biomarkers (IL-6, TNF-a, IL1, IL17, etc...) [Time Frame: Arm A; baseline, during treatment (Before every dose and 12 to 24 h post dose) up to 1 month, Arm B; baseline, 12 to 24 h and approx. 7 and 14 days after randomization]
2. Lymphocyte count [Time Frame: Arm A; baseline and before every dose up to 1 month, Arm B; baseline, approx. 7 and 14 days after randomization]
Lymphocyte count assessed by routinely used determination of blood count
3. PaO₂ (partial pressure of oxygen) / FiO₂ (fraction of inspired oxygen, FiO₂) ratio (or P/F ratio) [Time Frame: Arm A; baseline, during treatment (Before every dose and 48 h post dose) up to 1 month, Arm B: baseline, 48 h and approx. 7 and 14 days after randomization]
calculated from arterial blood gas analyses (values from 300 to 100)
4. Number of participants with treatment-related side effects as assessed by Common Terminology Criteria for Adverse Event (CTCAE) version 5.0 [Time Frame: during treatment and up to 30 days after the last treatment dose]*
graded according to CTCAE criteria (v5.0)
5. Radiological response [Time Frame: at baseline, after seven days and if clinically indicated (up to 1 month)]*
Thoracic CT scan or Chest XR
6. Duration of hospitalization [Time Frame: from baseline up to patient's discharge (up to 1 month)]*
Days of hospitalization and ICU
7. Remission of respiratory symptoms [Time Frame: up to 1 month]*
time to independence from non-invasive mechanical ventilation calculated in days
8. Remission of respiratory symptoms [Time Frame: up to 1 month]*
time to independence from oxygen therapy in days

* Applicable for both arms

6. Population

Patients who have tested positive for virological diagnosis of SARS-CoV2 infection (PCR) are planned to be randomised for enrolment from various centres in India.

Inclusion Criteria:

1. Male or female adults above 18 years (not tested in children yet)
2. Informed consent for participation in the study
3. Confirmed virological diagnosis of SARS-CoV2 infection (RT-PCR)
4. Hospitalized due to clinical worsening of COVID-19 infection
5. Oxygen saturation at rest in ambient air $\leq 94\%$

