Approximately 30 patients are considered sufficient to explore the study objectives and will be included in this study (number of patients may be increased if there is benefit observed in initial cohort of patients. There is no formal sample size calculation estimated).

Method of assigning patient to treatment group:

All eligible patients entering into the study will be randomized in 2:1 ratio to receive the treatment A/ B respectively. A computer derived randomization schedule is planned to be generated using appropriate system e.g. SAS to assign patient to treatment groups. Randomization will be central and appropriate system (e.g. remote telephone based, computer-based email, sealed envelope) will be used to distribute randomization schedule to the site

Note: If the patient is randomised to Arm A and is not initiated itolizumab or not administer one full infusion, is then not considered randomized. The same randomisation code will be used for the subsequent subject in that particular site.

Approximate number of sites:

1-10 sites

7. Treatment

Treatment Intervention and Dose:

Arm A: Best supportive care + Itolizumab

The best supportive care to be given as per the institutions protocol will be administered

(e.g: antivirals /antibiotics/ hydroxychloroquine; oxygen therapy, etc) + **Itolizumab**

Itolizumab

Note: Premedication: Hydrocortisone 100 mg i.v (or equivalent short acting glucocorticoid) and Pheniramine 30 mg per i.v. about 30 ± 10 minutes prior to infusion.

Start at 1.6 mg/kg dose iv infusion, if well tolerated, investigator has the discretion to continue with 1.6 mg/kg dose every 2 weeks or 0.8 mg/kg weekly regimen.

Subsequent dose and frequency can be modified, deferred or stopped if patient recovers as per investigator's discretion. If patients' overall parameters improve (if performed and RT-PCR is negative) further dose need not be given. Total infusion received during study duration can vary from 1 to 4 for each patient.

Arm B: Best supportive care

The best supportive care to be given as per the institutions protocol will be administered

(e.g: antivirals/antibiotics/ hydroxychloroquine; oxygen therapy, etc)

Dosing, Handling and Storage of Itolizumab

- Itolizumab is to be stored in 6R, USP type-1, 10 mL glass vials, refrigerated condition at 2°C to 8°C and is stable at that temperature for 36 months.

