**Biochemistry assessments (blood test) include blood urea, liver function tests (i.e. serum bilirubin, AST, ALT, ALP, Serum albumin), Lipid profile (including triglyceride), LDH, serum creatinine, Procalcitonin, d-Dimer, Trop-I, Ferritin. All blood samples for hematology and biochemistry must be collected prior to dosing, and additional as per investigator discretion.

Note: Hematology and Biochemistry including (Procalcitonin, d-Dimer, Trop-I, Ferritin, LDH and CRP) are recommended every 48 to 72 hours.

§: To be recorded daily: TLC; DLC, ANC, ALC; Platelet count; S. creatinine; T. Bilirubin; morning Vitals –pulse, BP, RR; Temperature (highest temperature of the day), PaO₂/FiO₂, MAP, GCS. These daily assessments are mandatory until patient moved out of ICU/equivalent. If patient is not admitted in the ICU/equivalent at the time of enrolment, then it is recommended to capture these assessments daily for first 7 days.

@ Premedication: **In arm A:** Hydrocortisone 100 mg i.v (or equivalent short acting glucocorticoid) and Pheniramine 30 mg per i.v. about 30 \pm 10 minutes prior to infusion.

To be repeated as suggested by the investigator in ICU setting. Earlier chest X ray report may be considered after discussing with sponsor.

d: Cytokine levels in serum: such as IFN- α , TNF- α , IL-17, IL-6, IL-1, IL-4, IL-2, IL-10, GM-CSF, IFN- γ at baseline, before every dose and 12-24 h after dose in Arm A. In Arm B, same panel will be assessed at baseline, 12 to 24 h and approx. 7 and 14 days after randomization. Immunophenotyping in whole blood samples: Teff cells (CD4, CD8, Treg cells), TH17 and macrophage activated cells will be analysed at baseline, 12-24 h after 1st dose and 24h after the second/last dose in Arm A and at baseline, 12-24 h and approx. 7 days after randomization in Arm B.

Timing of administration of Itolizumab:

Patients should be randomized in the trial and given Itolizumab who are in moderate to severe ARDS as defined by PaO₂/Fio₂ ratio of < 200 or more than 25% deterioration from the immediate previous value.

OR

Baseline serum ferritin level \geq 400 ng/mL or IL-6 levels greater than 4 times ULN, if known

Note: Either of Inclusion number 6 or 7 is required for inclusion of the patient into the study. Since there is logistical delay in getting results in time, biomarker data as inclusion criteria may be used if already known.

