### 3.2.2 Secondary endpoints

1. Biomarkers (IL-6, TNF-a, IL1, IL17, etc...) [ Time Frame: Arm A; baseline, during treatment (Before every dose and 12 to 24 h post dose) up to 1 month, Arm B; baseline, 12 to 24 h and approx. 7 and 14 days after randomization ]
2. Lymphocyte count [ Time Frame: Arm A; baseline and before every dose up to 1 month, Arm B; baseline, approx. 7 and 14 days after randomization ] Lymphocyte count assessed by routinely used determination of blood count
3. PaO2 (partial pressure of oxygen) / FiO2 (fraction of inspired oxygen, FiO2) ratio (or P/F ratio) [ Time Frame: Arm A; baseline, during treatment (Before every dose and 48 h post dose) up to 1 month, Arm B: baseline, 48 h and approx. 7 and 14 days after randomization] calculated from arterial blood gas analyses (values from 300 to 100)
4. Number of participants with treatment-related side effects as assessed by Common Terminology Criteria for Adverse Event (CTCAE) version 5.0 [ Time Frame: during treatment and up to 30 days after the last treatment dose ]\* graded according to CTCAE criteria (v5.0)
5. Radiological response [ Time Frame: at baseline, after seven days and if clinically indicated (up to 1 month) ]\* Thoracic CT scan or Chest XR
6. Duration of hospitalization [ Time Frame: from baseline up to patient's discharge (up to 1 month) ]\* Days of hospitalization and ICU

7. Remission of respiratory symptoms [ Time Frame: up to 1 month ]\* time to independence from non-invasive mechanical ventilation calculated in days
8. Remission of respiratory symptoms [ Time Frame: up to 1 month ]\* time to independence from oxygen therapy in days

\* Applicable for both arms

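### Cytokines are sampled around doses in Arm A but on fixed days in Arm B, so any between-arm comparison after 24 h depends on which Arm A patients are still being dosed

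*Protocol*

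**What the plan says.** **Arm A.** Protocol section 8.2 sets cytokine draws "at baseline, weekly before every dose and 12-24 h after dose in Arm A". Footnote d to the visit schedule in section 8.1 gives the same rule without the word *weekly*: "at baseline, before every dose and 12-24 h after dose in Arm A". SAP section 3.2.2, item 1, repeats it as a time frame: "Arm A; baseline, during treatment (Before every dose and 12 to 24 h post dose) up to 1 month". Secondary outcome 1 in Protocol section 5 matches the SAP.

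**Arm B.** Section 8.2 continues: "In Arm B, same panel will be assessed at baseline, 12 to 24 h and approx. 7 and 14 days after randomization".

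**Dosing in Arm A.** Protocol section 7 starts every patient on one infusion. It then leaves a two-weekly or a weekly regimen to the investigator and adds: "Total infusion received during study duration can vary from 1 to 4 for each patient". It also says: "If patients' overall parameters improve (if performed and RT-PCR is negative) further dose need not be given". Footnote b to section 8.1 repeats both sentences, but it words continuation as depending on good tolerance and on improvement having been observed.

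**Analysis.** SAP section 9 (Secondary Efficacy Evaluation) plans change from baseline in the biomarkers with a 95% confidence interval for the treatment difference. It names no day. SAP section 12 allows a missing laboratory value to be taken from within 2 days either side. Listing 16.1.8, the biomarker listing, has a visit column but only pre-dose and post-dose collection fields.

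**The concern.** A between-arm change needs both arms measured at a common time in groups that randomisation still makes comparable. After the first 24 h the plan secures neither for cytokines. Arm B's later draws come from the calendar. Arm A's come from a dosing decision that is made after randomisation and that the protocol links to how the patient is doing.

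An Arm A patient who has no second infusion has no cytokine draw scheduled beyond 12 to 24 h after the first. The confidence interval in SAP section 9, if computed on later values, would compare Arm B patients who could be sampled with Arm A patients who were still being dosed. The secondary objective also asks how immunomodulation relates to clinical improvement. If patients who improve stop dosing, they are the ones with the fewest cytokine values.

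**Working it through.** The plan states no figure on this point, and the sample size of about 30 has no formal calculation, so there is nothing to reproduce.

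**Step 1: schedule.** The dosing days are 1, 8, 15 and 22 (Protocol section 8.1). Each dose brings a pre-dose draw and one about a day later. The table counts a draw if it falls within 2 days of Day 7 or Day 14 (SAP section 12 window).

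| Arm A pattern | Scheduled draws (day) | Near Day 7 | Near Day 14 |
|---|---|---|---|
| 1 dose | 1, 2 | none | none |
| 2 doses, two-weekly | 1, 2, 15, 16 | none | 15, 16 |
| 2 doses, weekly | 1, 2, 8, 9 | 8, 9 | none |
| 3 doses, weekly | 1, 2, 8, 9, 15, 16 | 8, 9 | 15, 16 |
| 4 doses, weekly | 1, 2, 8, 9, 15, 16, 22, 23 | 8, 9 | 15, 16 |

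Counting Arm B's later draws as Days 8 and 15 gives the same pattern. A one-dose patient has 2 cytokine time points, against 4 in Arm B.

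**Step 2: precision.** About 30 patients at 2:1 gives 30 × 2/3 = 20 and 30/3 = 10. For a marker with standard deviation 1, the standard error of the difference in means is √(1/nA + 1/nB). The missing share of Arm A is an assumption, and Arm B is assumed to keep all 10.

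| Arm A without a sample | nA v nB | Standard error (SD) | Increase |
|---|---|---|---|
| 0% | 20 v 10 | √(0.0500 + 0.1) = 0.387 | – |
| 25% | 15 v 10 | √(0.0667 + 0.1) = 0.408 | 5% |
| 50% | 10 v 10 | √(0.1000 + 0.1) = 0.447 | 15% |
| 75% | 5 v 10 | √(0.2000 + 0.1) = 0.548 | 41% |

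This measures lost precision, not selection bias.

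**Step 3: how large selection could be.** Suppose there is no true effect, the most improved share f of Arm A goes unsampled, and clinical response correlates ρ with marker change. The expected spurious difference is approximately ρ × φ(z)/(1 − f) SD, where z is the f-quantile of the standard normal distribution and φ its density. For f = 0.5 and ρ = 0.5 this is 0.5 × 0.399/0.5 = 0.40 SD. A simulation (20 v 10 before loss, two-sided t-test at 5%, 20,000 runs, ρ from 0.3 to 0.7) gave:

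| f (assumed) | Spurious difference (SD) | Type I error |
|---|---|---|
| 25% | 0.12 to 0.28 | 6% to 12% |
| 50% | 0.23 to 0.54 | 8% to 24% |
| 75% | 0.36 to 0.85 | 9% to 33% |

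With everyone sampled the bias was 0.00 and the error about 5%. If the least improved stop instead, the size is the same and the sign reverses. The model makes every gap depend on response, so it shows what selection could do and is not an estimate for this trial.

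**The case against.** The other side has several good points.

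- **No later comparison is named.** A reader might infer that the SAP plans a Day 7 and Day 14 cytokine comparison. It does not: section 9 gives no day, and no table shows cytokines by visit. The 12 to 24 h draw exists in both arms and precedes any decision on redosing. It is not selected on continued dosing, although it is timed from dose in Arm A and from randomisation in Arm B. What remains is that Arm B has no other draws after 24 h, so any later contrast has to use those two days.
- **The objective is written around treatment.** It asks for biomarkers before and after itolizumab, which dose-timed sampling serves. That does not supply what the promised between-arm interval needs.
- **The word *weekly* in section 8.2.** It could be read as a weekly draw regardless of dosing. It is attached to the dose, and section 5, footnote d and the SAP omit it, so this reading is weak. The wording is at best ambiguous.
- **Selection is not purely by response.** Some Day 7 gaps come only from the two-week interval. Discharge, with telephone follow-up, and death cost samples in both arms.
- **Other markers are covered.** CRP, ferritin, d-Dimer, lymphocytes and PaO2/FiO2 are on the visit schedule in both arms, although their outcome time frames carry the same dose-tied wording.

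**Conclusion.** The point holds for the cytokine panel after the first 24 h. Followed as written, the plan leaves one-dose patients without a scheduled draw near either later Arm B time, and two-weekly patients without one near Day 7. A later between-arm interval would then rest on Arm A patients selected by continued dosing.

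A reader might go further and conclude that responders drop out of Arm A, so that the comparison is biased against itolizumab. The documents do not support a direction. Protocol section 7 lets patients who improve stop, while footnote b to section 8.1 makes continuation depend on improvement. Those passages must be reconciled.

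The loss of precision is 5% to 41% of the standard error for assumed missing shares of 25% to 75% with Arm B complete. The bias figures rest on further assumed correlations. For a secondary outcome in an exploratory trial of about 30 patients, this is a worthwhile, cheap improvement and does not threaten the trial as a whole.

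**What to change.** - In Protocol section 5 (secondary outcome 1), section 8.1 footnote d, section 8.2 and SAP section 3.2.2 item 1, schedule Arm A cytokine serum also at Day 8 and Day 15, within the existing visit window of 48 hours either side. This applies to every patient still attending, whether or not a dose is due. Use one wording in all four places, which also settles the word *weekly*.
- In SAP section 9, base the between-arm cytokine interval on 12 to 24 h, Day 8 and Day 15. Keep the other dose-timed samples as descriptive Arm A data.
- Give Listing 16.1.8 collection fields that do not depend on a dose. Report by arm the number sampled at each time and the reasons for missing samples.
- For CRP, ferritin, d-Dimer, lymphocytes and PaO2/FiO2, only align the outcome time-frame wording with the visit schedule.
- Reconcile section 7 with footnote b on what continued dosing depends on.

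The cost is protocol and SAP wording, plus one 4 to 5 mL tube and its assay per undosed Arm A patient per visit, at visits where blood is already scheduled. It changes no treatment. Samples lost to discharge or death in either arm are not recovered, so some selection can remain.

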1. The World Medical Association (WMA) has developed the Declaration of Helsinki as a statement of ethical principles for medical research involving human subjects, including research on identifiable human material and data.

The Declaration is intended to be read as a whole and each of its constituent paragraphs should be applied with consideration of all other relevant paragraphs.

2. Consistent with the mandate of the WMA, the Declaration is addressed primarily to physicians. The WMA encourages others who are involved in medical research involving human subjects to adopt these principles.

General Principles

3. The Declaration of Geneva of the WMA binds the physician with the words, “The health of my patient will be my first consideration,” and the International Code of Medical Ethics declares that, “A physician shall act in the patient's best interest when providing medical care.”

4. It is the duty of the physician to promote and safeguard the health, well-being and rights of patients, including those who are involved in medical research. The physician's knowledge and conscience are dedicated to the fulfilment of this duty.

5. Medical progress is based on research that ultimately must include studies involving human subjects.

6. The primary purpose of medical research involving human subjects is to understand the causes, development and effects of diseases and improve preventive, diagnostic and therapeutic interventions (methods, procedures and treatments). Even the best proven interventions must be evaluated continually through research for their safety, effectiveness, efficiency, accessibility and quality.

7. Medical research is subject to ethical standards that promote and ensure respect for all human subjects and protect their health and rights.

8. While the primary purpose of medical research is to generate new knowledge, this goal can never take precedence over the rights and interests of individual research subjects.

9. It is the duty of physicians who are involved in medical research to protect the life, health, dignity, integrity, right to self-determination, privacy, and confidentiality of personal information of research subjects. The responsibility for the protection of research subjects must always rest with the physician or other health care professionals and never with the research subjects, even though they have given consent.

10. Physicians must consider the ethical, legal and regulatory norms and standards for research involving human subjects in their own countries as well as applicable international norms and standards. No national or international ethical, legal or regulatory requirement should reduce or eliminate any of the protections for research subjects set forth in this Declaration.

11. Medical research should be conducted in a manner that minimises possible harm to the environment.

12. Medical research involving human subjects must be conducted only by individuals with the appropriate ethics and scientific education, training and qualifications. Research on patients or healthy volunteers requires the supervision of a competent and appropriately qualified physician or other health care professional.

13. Groups that are underrepresented in medical research should be provided appropriate access to participation in research.

14. Physicians who combine medical research with medical care should involve their patients in research only to the extent that this is justified by its potential preventive, diagnostic or therapeutic value and if the physician has good reason to believe that participation in the research study will not adversely affect the health of the patients who serve as research subjects.

15. Appropriate compensation and treatment for subjects who are harmed as a result of participating in research must be ensured.

Risks, Burdens and Benefits

16. In medical practice and in medical research, most interventions involve risks and burdens.

Medical research involving human subjects may only be conducted if the importance of the objective outweighs the risks and burdens to the research subjects.

17. All medical research involving human subjects must be preceded by careful assessment of predictable risks and burdens to the individuals and groups involved in the research in comparison with foreseeable benefits to them and to other individuals or groups affected by the condition under investigation.

Measures to minimise the risks must be implemented. The risks must be continuously monitored, assessed and documented by the researcher.

18. Physicians may not be involved in a research study involving human subjects unless they are confident that the risks have been adequately assessed and can be satisfactorily managed.

When the risks are found to outweigh the potential benefits or when there is conclusive proof of definitive outcomes, physicians must assess whether to continue, modify or immediately stop the study.

Vulnerable Groups and Individuals

19. Some groups and individuals are particularly vulnerable and may have an increased likelihood of being wronged or of incurring additional harm.

All vulnerable groups and individuals should receive specifically considered protection.

20. Medical research with a vulnerable group is only justified if the research is responsive to the health needs or priorities of this group and the research cannot be carried out in a non-vulnerable group. In addition, this group should stand to benefit from the knowledge, practices or interventions that result from the research.

Scientific Requirements and Research Protocols

21. Medical research involving human subjects must conform to generally accepted scientific principles, be based on a thorough knowledge of the scientific literature, other relevant sources of information, and adequate laboratory and, as appropriate, animal experimentation. The welfare of animals used for research must be respected.

22. The design and performance of each research study involving human subjects must be clearly described and justified in a research protocol.

The protocol should contain a statement of the ethical considerations involved and should indicate how the principles in this Declaration have been addressed. The protocol should include information regarding funding, sponsors, institutional affiliations, potential conflicts of interest, incentives for subjects and information regarding provisions for treating and/or compensating subjects who are harmed as a consequence of participation in the research study.

In clinical trials, the protocol must also describe appropriate arrangements for post-trial provisions.

Research Ethics Committees

23. The research protocol must be submitted for consideration, comment, guidance and approval to the concerned research ethics committee before the study begins. This committee must be transparent in its functioning, must be independent of the researcher, the sponsor and any other undue influence and must be duly qualified. It must take into consideration the laws and regulations of the country or countries in which the research is to be performed as well as applicable international norms and standards but these must not be allowed to reduce or eliminate any of the protections for research subjects set forth in this Declaration.

The committee must have the right to monitor ongoing studies. The researcher must provide monitoring information to the committee, especially information about any serious adverse events. No amendment to the protocol may be made without consideration and approval by the committee. After the end of the study, the researchers must submit a final report to the committee containing a summary of the study's findings and conclusions.

Privacy and Confidentiality

24. Every precaution must be taken to protect the privacy of research subjects and the confidentiality of their personal information.

Informed Consent

25. Participation by individuals capable of giving informed consent as subjects in medical research must be voluntary. Although it may be appropriate to consult family members or community leaders, no individual capable of giving informed consent may be enrolled in a research study unless he or she freely agrees.

26. In medical research involving human subjects capable of giving informed consent, each potential subject must be adequately informed of the aims, methods, sources of funding, any possible conflicts of interest, institutional affiliations of the researcher, the anticipated benefits and potential risks of the study and the discomfort it may entail, post-study provisions and any other relevant aspects of the study. The potential subject must be informed of the right to refuse to participate in the study or to withdraw consent to participate at any time without reprisal. Special attention should be given to the specific information needs of individual potential subjects as well as to the methods used to deliver the information.

After ensuring that the potential subject has understood the information, the physician or another appropriately qualified individual must then seek the potential subject's freely-given informed consent, preferably in writing. If the consent cannot be expressed in writing, the non-written consent must be formally documented and witnessed.

All medical research subjects should be given the option of being informed about the general outcome and results of the study.

27. When seeking informed consent for participation in a research study the physician must be particularly cautious if the potential subject is in a dependent relationship with the physician or may consent under duress. In such situations the informed consent must be sought by an appropriately qualified individual who is completely independent of this relationship.

28. For a potential research subject who is incapable of giving informed consent, the physician must seek informed consent from the legally authorised representative. These individuals must not be included in a research study that has no likelihood of benefit for them unless it is intended to promote the health of the group represented by the potential subject, the research cannot instead be performed with persons capable of providing informed consent, and the research entails only minimal risk and minimal burden.

29. When a potential research subject who is deemed incapable of giving informed consent is able to give assent to decisions about participation in research, the physician must seek that assent in addition to the consent of the legally authorised representative. The potential subject's dissent should be respected.

30. Research involving subjects who are physically or mentally incapable of giving consent, for example, unconscious patients, may be done only if the physical or mental condition that prevents giving informed consent is a necessary characteristic of the research group. In such circumstances the physician must seek informed consent from the legally authorised representative. If no such representative is available and if the research cannot be delayed, the study may proceed without informed consent provided that the specific reasons for involving subjects with a condition that renders them unable to give informed consent have been stated in the research protocol and the study has been approved by a research ethics committee. Consent to remain in the research must be obtained as soon as possible from the subject or a legally authorised representative.

31. The physician must fully inform the patient which aspects of their care are related to the research. The refusal of a patient to participate in a study or the patient's decision to withdraw from the study must never adversely affect the patient-physician relationship.

32. For medical research using identifiable human material or data, such as research on material or data contained in biobanks or similar repositories, physicians must seek informed consent for its collection, storage and/or reuse. There may be exceptional situations where consent would be impossible or impracticable to obtain for such research. In such situations the research may be done only after consideration and approval of a research ethics committee.

Use of Placebo

33. The benefits, risks, burdens and effectiveness of a new intervention must be tested against those of the best proven intervention(s), except in the following circumstances:

Where no proven intervention exists, the use of placebo, or no intervention, is acceptable; or

Where for compelling and scientifically sound methodological reasons the use of any intervention less effective than the best proven one, the use of placebo, or no intervention is necessary to determine the efficacy or safety of an intervention and the patients who receive any intervention less effective than the best proven one, placebo, or no intervention will not be subject to additional risks of serious or irreversible harm as a result of not receiving the best proven intervention.

Extreme care must be taken to avoid abuse of this option.

Post-Trial Provisions

34. In advance of a clinical trial, sponsors, researchers and host country governments should make provisions for post-trial access for all participants who still need an intervention identified as beneficial in the trial. This information must also be disclosed to participants during the informed consent process.

Research Registration and Publication and Dissemination of Results

35. Every research study involving human subjects must be registered in a publicly accessible database before recruitment of the first subject.

36. Researchers, authors, sponsors, editors and publishers all have ethical obligations with regard to the publication and dissemination of the results of research. Researchers have a duty to make publicly available the results of their research on human subjects and are accountable for the completeness and accuracy of their reports. All parties should adhere to accepted guidelines for ethical reporting. Negative and inconclusive as well as positive results must be published or otherwise made publicly available. Sources of funding, institutional affiliations and conflicts of interest must be declared in the publication. Reports of research not in accordance with the principles of this Declaration should not be accepted for publication.

Unproven Interventions in Clinical Practice

37. In the treatment of an individual patient, where proven interventions do not exist or other known interventions have been ineffective, the physician, after seeking expert advice, with informed consent from the patient or a legally authorized representative, may use an unproven intervention if in the physician's judgment it offers hope of saving life, re-establishing health or alleviating suffering. This intervention should subsequently be made the object of research, designed to evaluate its safety and efficacy. In all cases, new information must be recorded and, where appropriate, made publicly available.

